8.5 Warnings and precautions

No evidence available at the time of the approval of this protocol indicated that special warnings or precautions were appropriate. [REDACTED] or Product Label.

[REDACTED] his information will be included in the patient informed consent and should be discussed with the patient during the study as needed.

Patients will have blood drawn for clinical labs, PK and PD through direct venipuncture, whenever possible. Venipuncture may cause some pain, bleeding or bruising where the needle entered the patient's body. Some patients may have an intravenous (IV) catheter placed or a midline catheter for blood collection, as determined needed by the investigator. Placing an IV may cause some pain, and bleeding or bruising at the spot where the needle entered the patient's body. There may also be a risk of irritation of the vein (phlebitis), infection, blood clot, leakage or infiltration and/or nerve or tendon injury during insertion. Care will be taken to avoid these problems. The longer an IV catheter is left in place, the more common it is for redness or infection to develop. This information will be included in the patient informed consent and discussed with the patient as needed.

8.6 Data and Safety Monitoring Board

A group of experts will be assembled to assess the progress, safety data and, if needed critical efficacy endpoints of the study as part of a Data and Safety Monitoring Board. Safety and toxicity will be assessed throughout the study duration, including preoperative and peri-operative time periods. The DSMB charter will be documented in a separate document. Study stopping rules are, if two or more patients have a \geq 4 week delay to surgery due to ribociclib or everolimus related toxicity, the study will be stopped. Also see Table 8 for additional stopping rules. Based on its

review, the DSMB will provide recommendations regarding study modification, continuation or termination.

8.6.1 Dose Escalations

At the time of dose escalation, a written report will be submitted to the DSMB Chair (or qualified alternate) describing the cohorts, dose levels, adverse events, safety reports and any DLTs observed. The DSMC Chair will review the report and provide a written authorization to proceed or request more information within 2 business days. Approval for the dose escalation must be obtained prior to implementation.

9 Data collection and management

9.1 Site monitoring

The Ivy Brain Tumor Center (IBTC) will be the monitoring entity for this study. A monitor from IBTC will audit study-related activities to ensure the study is conducted in accordance with the protocol, local standard operating procedures, FDA regulations and Good Clinical Practice (GCP).

9.2 Data confidentiality, collection, management, and quality control

All databases will be kept on a password-protected, HIPAA-compliant computer system, REDCap Cloud. REDCap is a secure web application with authentication and data logging. Only authorized study personnel will have access to the study data. Individually-identifiable health information will be protected by assignment of patient identifiers and password-protection of the key. Only the Investigators and the Research will have access to this database. All biological specimens will be de-identified and assigned the corresponding patient code from which they are derived.

9.3 Analysis sets

9.3.1 Full Analysis Set

The statistical analysis of the data obtained from this study will be the responsibility of the Clinical Biostatistics division of the Ivy Brain Tumor Center (IBTC).

9.4 Patient demographics/other baseline characteristics

The comparability of the treatment groups for each relevant characteristic will be assessed by the use of tables and/or graphs. No statistical hypothesis tests will be performed on these characteristics. The number and percentage of patients screened, randomized, the primary reasons for screening failure, and the primary reason for discontinuation will be displayed. Demographic variables (such as age) and baseline characteristics will be summarized by treatment either by descriptive statistics or categorical tables. The reasons for exclusion from the Full Analysis Set (if any) will be summarized.

9.5 Primary objective

	Objective	Endpoint
Primary	
 • To determine the dose-limiting toxicity (DLT) and maximum tolerated dose (MTD) for study drug when administered in combination. • To identify recurrent high-grade glioma patients with positive PK and PD effects. 	
 • MTD: highest dose of drug that did not cause a DLT in > 17% of participants • PK: total and unbound ribociclib and everolimus drug concentrations in non-enhancing and contrast-enhancing tumor tissue samples • PD: pRB-positive cells and pS6-positive cells

9.6 Secondary and exploratory objectives

	Objective	Endpoint
Secondary	
 • To explore safety and efficacy in recurrent high-grade glioma patients with demonstrated PK and PD effects and determine RP2D • To describe PK for Phase 2 patients 	
 • Progression-free survival (PFS): rate measured from time of surgery to date of recurrence • Overall survival (OS): Median Overall Survival (OS) from time of surgery to date of death from any cause • Drug-related toxicity • RP2D • Systemic PK profiles of ribociclib and everolimus when combined.
Exploratory	
 • To explore evidence for CDK4/6 and mTOR pathway activity in tumor tissue (as compared to archival tissue) and mechanisms of resistance • Pharmacometabolomics: To explore the plasma metabolomic signature of the exposure of ribociclib and everolimus 	
 • Quantification of total and phosphorylated forms of Rb, FoxM1, S6, 4EBP, as well as cleaved Caspase-3 and MIB1. Expression of Cyclin D1, Cyclin E1, PI3K/mTOR signaling components • Plasma metabolomic profiles (i.e., levels of ~250 metabolites) at the pretreatment and at predefined time points after the combination therapy. • Pharmacogenomics studies using RNA-seq and Whole Exome Sequencing to identify alterations in gene expression and mutational profile between pre-

	
• To identify resistance mechanism and alternate pathways	treatment and post-treatment tissues and plasma.
--	---	--

9.6.1 Statistical hypothesis, model, and method of analysis

If, after the study has begun, changes are made to primary and/or key secondary hypotheses, or the statistical methods related to those hypotheses, then the protocol will be amended. Changes to exploratory or other non-confirmatory analyses made after the protocol has been finalized, along with an explanation as to when and why they occurred, will be listed in results for the study. Post hoc exploratory analyses will be clearly identified. No separate Statistical Analysis Plan (SAP) will be issued for this study.

9.6.2 Safety objectives

Safety measurements are described in [7.2.2](#).

9.6.3 Adverse Events (AEs)

Adverse events (AEs) are described in [8.1](#).

9.7 Statistical Methods

All continuous variables (e.g., drug concentrations in plasma and high-grade glioma tissue, and any continuous PD biomarkers, and their pre/post treatment change) will be summarized with standard descriptive statistics (N, median, mean, standard deviation, minimum, maximum, and the 80% confidence interval [CI] for the mean). The 80% confidence level is appropriate for a Phase 0 study with small sample sizes.

These continuous variables will be summarized by time interval and overall. Statistical graphics (e.g., boxplots and scatterplots) will be used as appropriate. The pre/post treatment changes (as % change variables) will also be displayed as waterfall plots. All categorical variables (e.g., PD parameters such as scoring of Rb phosphorylation staining intensity: 0, 1, 2, or 3) will be summarized as frequency distributions. If dichotomized (e.g., score 2 or higher), those proportions will be described by point estimates and 80% CIs using the Wilson's method. These categorical variables will be summarized by time interval, and overall. The pre/post treatment changes in categorical variables (whether dichotomized or not) will be displayed as 2-way frequency distributions (i.e., contingency tables).

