In Dose Levels 2+, three to six patients will be enrolled into cohort 2. If there are positive PK/PD results at the Maximum Tolerated Dose (MTD) or Optimal Biological Dose (OBD) dose level, the dose level will be expanded to 8 additional patients with 4 patients in each time cohort 1 and 3 (Sections [6.1.2](#) and [6.1.2.1](#)).

Dose Level	Time Interval	N=	Dose Expansion Cohort N=	Time Cohort Expansion N=
Level 0	Cohort 1	2	N/A	N/A
	Cohort 2	2		
	Cohort 3	2		
Level 1	Cohort 1	1	0	4
	Cohort 2	2	3	0
	Cohort 3	0	0	4
Level 2	Cohort 1	0	0	4
	Cohort 2	3	3	0
	Cohort 3	0	0	4
Level 3	Cohort 1	0	0	4
	Cohort 2	3	3	0
	Cohort 3	0	0	4
Level 4 - 6	Cohort 1	0	0	4
	Cohort 2	3	3	0
	Cohort 3	0	0	4

To assess the PK and PD endpoints listed above, blood, CSF and brain tumor tissue will be collected intraoperatively (enhancing and non-enhancing tumor tissue will be collected and analyzed separately).

Additionally, blood samples will be obtained on Day 4 in Dose Levels 1-3 (the day before the surgery for Cohorts 1 & 2; 2 days before surgery for Cohort 3) at pre-dosing (trough level), 0.5, 1, 2, 4, 7, and 24 hours post dose. (Note: 24 h sample is the pre-dosing (trough level) blood sample on Day 5).

Dose Level 4+ only: PK blood sampling will occur on Day 5: pre, 0.5, 1, 2, 4, 6, 8 and 24 hours post-dose (Note: 24 h sample is the pre-dosing (trough level) blood sample on Day 6).

Dose Levels 0-3:

[figure not shown]
PHASE 0 STUDY COHORT 1										
DAY 4 PRE- DOSE	Time 0	30 min	1 hour	2 hours	3 hours	4 hours	7 hours	24 hours ± 1 h	POSTOP- Phase 2	
Blood			Blood	Blood	Blood		Blood	Blood	Blood	
DAY 5 PRE- DOSE	Ribociclib + everolimus								Ribociclib + everolimus	
Blood			Blood* CSF* Tumor*							

PHASE 0 STUDY COHORT 2										
DAY 4 PRE- DOSE	Time 0	30 min	1 hour	2 hours	4 hours	7 Hours	8-9 Hours	24 hours ± 1 h	POSTOP- Phase 2	
Blood			Blood	Blood	Blood	Blood	Blood		Blood	
DAY 5 PRE- DOSE	Ribociclib + everolimus								Ribociclib + everolimus	
Blood			Blood* CSF* Tumor*							

PHASE 0 STUDY COHORT 3										
DAY 4 PRE- DOSE	Time 0	30 min	1 hour	2 hours	4 hours	7 Hours	23 -25 hours	POSTOP- Phase 2		
Blood	Ribociclib + everolimus		Blood	Blood	Blood	Blood	Blood	Blood	Ribociclib + everolimus	

Initial Version date: 10/16/2018

Revision date: 03/11/2019, 5/07/2019, 09/26/2019, 03/17/2020, 08/26/2024

[figure not shown]

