5.3 Exclusion criteria

Patients eligible must not meet **any** of the following criteria:

1. Archival tissue is not available for research use or there is not a sufficient quantity available to confirm eligibility.
2. Archival tumor is not Rb-positive status and mTOR-positive status.
3. Patient has not received prior radiotherapy.
4. Co-morbid condition(s) that, at the opinion of the investigator, prevent safe surgical treatment.
5. Active infection or fever $> 38.5^{\circ}\text{C}$ that in the opinion of the investigator would be a safety risk to the patient.
6. Active (acute or chronic) or uncontrolled severe infection, liver disease such as cirrhosis, decompensated liver disease, and active and chronic hepatitis (i.e. quantifiable HBV-DNA and/or positive HbsAg, quantifiable HCV-RNA).
7. Known severely impaired lung function (spirometry and DLCO 50% or less of normal and O₂ saturation 88% or less at rest on room air).
8. Active, bleeding diathesis.
9. Patients with known hypersensitivity to any of the excipients of ribociclib or mTOR inhibitors (sirolimus or everolimus), including peanut, soy and lactose.
10. Patients with a clinically significant hypersensitivity to everolimus or to other rapamycin derivatives.
11. Prior therapy with ribociclib or any CDK4/6 inhibitor (e.g. palbociclib, abemaciclib), or with everolimus. Prior therapy is defined as a therapeutic dosing.
12. Patient who has received radiotherapy ≤ 4 weeks or limited field radiation for palliation ≤ 2 weeks prior to starting study drug, and who has not recovered to grade 1 or better from related side effects of such therapy (exceptions include alopecia or other toxicities not considered a safety risk for the patient at investigator's discretion) and/or in whom $\geq 25\%$ of the bone marrow (Ellis, 1961) was irradiated.
13. Patient has a concurrent malignancy or malignancy within 3 years prior to starting study drug, with the exception of adequately treated, basal or squamous cell carcinoma, non-melanomatous skin cancer or curatively resected cervical cancer.
14. Patient has impairment of gastrointestinal (GI) function or GI disease that may significantly alter the absorption of the study drugs (e.g., ulcerative diseases, uncontrolled nausea, vomiting, diarrhea, malabsorption syndrome, or small bowel resection).
15. Patient has a known history of HIV infection (seropositivity; testing not mandatory).

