6.1.1 Phase 0 & 2 Dose Escalation Schedule

Table 7 Dose Escalation Schedule

Dose Level	Phase 0 Dose of Study Drug ^a	Minimum Number of Patients	Phase 2 Dose of Study Drug ^a
0	ribociclib 400mg and everolimus 2.5mg	6	ribociclib 400mg and everolimus 2.5mg
1	ribociclib 600mg and everolimus 2.5mg	3	ribociclib 600mg and everolimus 2.5mg

Initial Version date: 10/16/2018

Revision date: 03/11/2019, 5/07/2019, 09/26/2019, 03/17/2020, 08/26/2024

Dose Level	Phase 0 Dose of Study Drug ^a	Minimum Number of Patients	Phase 2 Dose of Study Drug ^a
2	ribociclib 600mg and everolimus 5mg	3	ribociclib 600mg and everolimus 5mg
3	ribociclib 600mg and everolimus 10mg ^b	3	ribociclib 600mg and everolimus 10mg ^c
4	ribociclib 600mg, qd and everolimus 50mg once ^d	3	ribociclib 600mg daily and everolimus 50mg once weekly ^e
5	ribociclib 600mg, qd and everolimus 60mg once ^d	3	Cycle 1: ribociclib 600mg, qd and everolimus 50mg once weekly ^e Cycle 2+: 600 mg, qd and everolimus 60mg once weekly ^f
6	ribociclib 600mg, qd and everolimus 70mg once ^d	3	Cycle 1: ribociclib 600mg, qd and everolimus 50mg once weekly ^e Cycle 2: 600 mg, qd and everolimus 60mg once weekly ^f Cycle 3+: 600 mg, qd and everolimus 60mg once weekly ^f

- a. The Phase 0 dose given to the patient will be the RP2D. If more than one DLT is observed in 6 patients in Phase 2, the regimen at that given level will be considered as the maximal administered dose and the next lower dose level will be the MTD/RP2D for subsequent patients enrolled into Phase 2
- b. In Phase 0, the everolimus dose will be given in one dose (10mg, qd).
- c. In Phase 2, dose will be given in two doses (5mg, bid)
- d. In Phase 0, the everolimus dose will be given in one dose on Day 5 only; ribociclib dose will be given daily for 5 days.
- e. In Phase 2, everolimus dose will be given once weekly on Days 1, 8, 15, 22 of each cycle with ribociclib administered daily for 21 consecutive days and 1 rest week.
- f. If the dose is well tolerated in Cycle 1, the dose may be escalated based on investigator discretion.

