2	Screening assessment may be completed at Day 1 predose, if completed at screening, does not need to be repeated at Day 1 pre-dose except for ECG and ECOG. Results must be available to confirm eligibility prior to dosing.											
3	Estimated glomerular filtration rate (eGFR)											
4	ECG Day 1 Pre-dose, Day 1: 2-4 hrs post-dose, and pre-surgical assessment (can be completed on Day 4 or Day 5 (Cohort 1&2) / Day 6 (Cohort 3)).											
5	ECG Pre-dose and 2-4 hours post dose on C1D15, C2D15, C3D1, C6D1; C9D1; and every 3 rd cycle...											
6	ECG Pre-dose C2D1, C4D1, C5D1; C7D1, C8D1, C10D1, C11D1; and every 1st and 2nd cycle...											
7	Performed at pre-surgical assessment as per SOC on Day 4 (can be completed on Day 5 (Cohort 1&2) or Day 6 (Cohort 3)).											
8	Lipid panel performed every 4th cycle D1											
9	Study drugs are administered in the clinics on D1, D4 and D5. Patients may take medications at home on D2 and D3											
10	Trough blood sample is collected prior to the drug administration on that day. Study drugs are administered in the clinics on the clinic visit days 1, 8, 15, 22.											
11	Blood samples will be obtained on Day 4 (the day before the surgery for Cohorts 1 & 2; 2 days before surgery for Cohort 3) at pre-dosing (trough level), 0.5, 1, 2, 4, 7 hours post dose (\pm 5 min window for 0.5hr and 1hr; \pm 15min window for 2, 4, 7hr samples). A pre-dosing (trough level) blood sample will also be obtained on Day 5 and a sample will be collected intra-operatively. In Dose Level 4+ only, PK blood sampling will occur at the same timepoints (pre, 0.5, 1, 2, 4, 6, 8 and 24) but will be obtained on Day 5 (the day of surgery); the 24 hour sample will be obtained on Day 6.											
12	Only Patients that have a recurrence and undergo an additional surgery for tumor resection											
13	The start of follow up for long-term survival begins following completion of the Day 30 safety follow up call. Subjects will continue to be followed until death or withdrawal of consent for the collection and reporting of data or lost to follow-up for up to 5 years. Public records may be used to collect survival data, i.e., obituary notices and public database searches for survival information.											

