7.1.1.11.1 Day 1 Enrollment

The following assessments will be performed on Day 1:

- Review of surgical and medical procedures
- ECOG
- 12-lead ECG
- Collection of AEs and Concomitant medication(s)
- Screening assessments not previously collected as noted in section [7.1.1.9](#)
- Day 1 pre-dose PK sample
- Day 1 pre-dose biomarker blood sample
- Confirm eligibility prior to study drug administration
- In clinic/hospital study drug administration
- Provide the patient the following for home dosing on Days 2 and 3
 - Instructions for study medication
 - Dosing Diary
 - Symptom Diary
 - Study drug

7.1.1.11.2 Day 2 and 3

Phase 0 patients will record study drug administration in the Dosing Diary and record symptoms in the Symptom Diary.

7.1.1.11.3 Day 4

The following assessments will be performed on Day 4:

- Review of medical and surgical procedures
- Collection of AEs and Concomitant medication(s)
- Review of home dosing diary and symptom diary

- 12-lead ECG
- Trough PK Sample (Dose Levels 0-3)
- Laboratory testing (may also be performed as a pre-surgical assessment on Day 5 or Day 6):
 - Chemistry, (comprehensive metabolic panel, magnesium, phosphorus)
 - Hematology (CBC w/differential)
 - Coagulation (PT/INR, aPTT)
 - eGFR
- In clinic/hospital study drug administration
- PK blood sampling: 0.5, 1, 2, 4, 7 hours post-dose (Dose Levels 0-3)
 - *In Dose Level 4+ only, PK blood sampling will occur on Day 5 instead of Day 4.*

7.1.1.11.4 **Day 5**

- Review of medical and surgical procedures
- Collection of AEs and Concomitant medication(s)
- 12-Lead ECG (if not collected on Day 4)
- In clinic/hospital study drug administration
- Craniotomy (Day 5 for Cohort 1 & 2; Day 6 for Cohort 3)
 - PK Collection of blood, CSF and tumor
 - Biomarker tumor collection
- Dose Level 1-3: Day 5 trough/24hrs post-dose
- Dose Level 4+ only: PK blood sampling: pre, 0.5, 1, 2, 4, 6, 8 and 24 hours (Day 6) post-dose

7.1.1.11.5 **Follow-up / EOT visit**

Phase 0 patients will have a follow up visit 7-14 days after surgery (routine post-operative visit). All Phase 2 patients should be scheduled for an EOT visit within 7 (± 3) days following discontinuation of study treatment.

The following assessments will be performed at the EOT visit:

- Physical exam
- ECOG performance status
- Weight
- Vital signs
- Laboratory blood collections
 - CMP, magnesium, phosphorus
 - Hematology (CBC w/differential)
 - Urine pregnancy test (if applicable)
- 12-lead ECG

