9.7.1 Objectives, endpoints, analysis, and sample size justification

The primary objective of Phase 0 dose escalation and expansion studies is to determine the MTD and to identify patients with positive PK and PD effects and the key secondary objective is to explore the clinical effect of everolimus plus ribociclib in recurrent GBM patients. The exploratory objectives are to explore pharmacometabolomics (PM) markers, mechanisms of resistance, and to examine evidence for CDK4/6 and mTOR pathway activity described in the

previous section. The primary endpoints are MTD as well as PK and PD effects, which are for the Phase 0 component, and the progression-free survival (PFS) is a key secondary endpoint, which are for the Phase 2 dose expansion component. Other endpoints for the secondary objective are RP2D, overall survival (OS) and drug-related toxicity. In particular, the positive PK effect will be defined as unbound ribociclib and everolimus drug concentrations in non-enhancing tumor tissue $>$ *in vitro* IC50 of each agent. The positive PD effect will be defined as $>30\%$ decrease in pRB-positive cells and $>30\%$ decrease in pS6-positive cells. The PFS will be defined as the time duration from the date of surgery to disease progression or death from any cause and the OS the time duration from date of surgery to death from any cause. A Kaplan-Meier (KM) curve will be used to summarize the distributions of survival outcomes (PFS and OS) and the median PFS/OS and their associated 95% confidence interval (CI) will be estimated using KM estimates.

This study will be prospectively conducted as an open-label, multi-institution study (up to 3 sites) with four dose escalation and three time-escalation cohorts in the Phase 0 component and exploratory efficacy study in the dose expansion component. Patient assigned to one of the four dose escalation levels in Phase 0 will be assigned to one of three time-escalation cohorts in turn with 1 patient being placed into cohort 1, then 1 patient into cohort 2, and then 1 patient into cohort 3 and so on. Approximately 8 subjects in each cohort will be enrolled.

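### Section 9.7 groups the PK/PD summaries by time interval and overall but not by dose level, so if Levels 4-6 open the everolimus and pS6 tables mix daily dosing with a single Day 5 dose

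*Combined protocol and SAP*

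**What the plan says.** Section 9.7 (Statistical Methods) covers drug concentrations, continuous PD biomarkers and their pre/post changes, with 80% confidence intervals. On grouping it says "These continuous variables will be summarized by time interval and overall" and, for categorical PD variables and dichotomised proportions, "These categorical variables will be summarized by time interval, and overall". Within Section 9, only demographics and baseline characteristics are summarised by treatment (Section 9.4). Section 9.6.1 says that no separate SAP will be issued.

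The everolimus schedule changes during escalation. Section 4.1.1 and Table 7 give 2.5, 2.5, 5 and 10 mg daily for five days at Levels 0-3, and 50, 60 and 70 mg at Levels 4, 5 and 6. For the latter, a Table 7 footnote says "In Phase 0, the everolimus dose will be given in one dose on Day 5 only". Section 2.3 attributes the change to persistently negative everolimus PK results. Ribociclib is 400 mg at Level 0 and 600 mg at every other level.

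Blood sampling moves with the schedule: "Dose Level 4+ only: PK blood sampling will occur on Day 5". At lower levels the serial samples are taken on Day 4 and the pre-dose sample is called a trough (Sections 4.1.1 and 7.1.1.11.3).

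Tumour drug concentrations and pRB- and pS6-positive cells are primary endpoints (Section 9.5). In Section 9.7.1, "the positive PK effect will be defined as unbound ribociclib and everolimus drug concentrations in non-enhancing tumor tissue" above the in vitro IC50 of each agent. PD-positive status needs a fall of more than 30% in both pRB- and pS6-positive cells. Section 6.1.2.1 asks whether biological effect increases with dose.

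**The concern.** The stated grouping does not contain the factor that varies by design. Time interval would help only if the two everolimus schedules fell in different time cohorts, and they do not: Levels 2 to 6 all enter Cohort 2. The Cohort 2 and overall rows for everolimus concentration and pS6 would therefore average patients on five days of low-dose everolimus with patients who took one much larger dose hours before surgery. PK-positive status needs both drugs, and PD-positive status needs pS6 as well as pRB, so both proportions carry the same mixture.

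Two things are at stake in reporting the primary PK/PD endpoints. The means, proportions and 80% intervals may describe neither schedule. The planned tables also cannot display the dose-effect relation that Section 6.1.2.1 asks about.

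Ribociclib is affected differently. Its dose changes only once, but under the Section 4.1.1 table the 400 mg patients make up most of the small Cohorts 1 and 3. A comparison of ribociclib across time intervals is then partly a comparison of doses.

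**Working it through.** The plan states no figure for this point, so the check is a count of who falls in each planned row, followed by an illustration.

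**1. Inputs.** Patients before expansion, from the Section 4.1.1 table and the Table 7 minimums:

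| Level | Everolimus in Phase 0 | Ribociclib | Cohort 1 / 2 / 3 |
|---|---|---|---|
| 0 | 2.5 mg daily | 400 mg | 2 / 2 / 2 |
| 1 | 2.5 mg daily | 600 mg | 1 / 2 / 0 |
| 2 | 5 mg daily | 600 mg | 0 / 3 / 0 |
| 3 | 10 mg daily | 600 mg | 0 / 3 / 0 |
| 4, 5, 6 (each) | 50, 60, 70 mg once | 600 mg | 0 / 3 / 0 |

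Total through Level 6: 6 + 6 × 3 = 24.

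**2. Everolimus schedule within each planned row.**
- Cohort 2: daily 2 + 2 + 3 + 3 = 10; single-dose 3 × 3 = 9.
- Overall: daily 3 + 10 + 2 = 15; single-dose 9.
- Cohorts 1 and 3: 3 and 2 daily patients, with no single-dose patients before expansion. If one of Levels 4-6 receives the time-cohort expansion (4 each in Cohorts 1 and 3), they become 3 daily with 4 single-dose, and 2 with 4.
- If escalation stops after three patients at Level 4: 10 and 3 in Cohort 2; 15 and 3 overall.
- Section 6.1.2 requires at least 6 treated patients for an MTD. Naming Level 6 therefore needs at least 27 patients, 15 daily and 12 single-dose.

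**3. Sensitivity to the allocation rule.** Section 6.4.2 describes rotation with at least one patient per time interval at each level. With 2/2/2 at Level 0 and 1/1/1 at Levels 1-6, each cohort has 8 patients: 2 + 3 = 5 daily and 3 single-dose. Overall is still 15 and 9. The mixture then appears in every cohort without expansion.

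**4. Nominal everolimus dose in Cohort 2.** Daily: (2 × 2.5 + 2 × 2.5 + 3 × 5 + 3 × 10)/10 = 5.5 mg. Single-dose: (3 × 50 + 3 × 60 + 3 × 70)/9 = 60 mg. Pooled: (55 + 540)/19 = 31.3 mg, which is no patient's dose.

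**5. Ribociclib by time interval (Section 4.1.1 table, before expansion).** Patients at 400 mg: 2 of 3 in Cohort 1, 2 of 19 in Cohort 2, 2 of 2 in Cohort 3. Under the rotation in step 3 it would be 2 of 8 in each, so this confounding depends on the Section 4.1.1 table being followed.

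**6. Illustration for the proportion PK-positive, overall row.** The response counts are assumptions; the documents give none. Pooled proportion = (daily positives + single-dose positives)/24:

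| Daily positives | 3/9 single-dose (33%) | 5/9 (56%) | 7/9 (78%) |
|---|---|---|---|
| 0/15 (0%) | 13% | 21% | 29% |
| 3/15 (20%) | 25% | 33% | 42% |
| 6/15 (40%) | 38% | 46% | 54% |

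The 80% Wilson interval is (p + z²/2n ± z√(p(1−p)/n + z²/4n²))/(1 + z²/n), with z = 1.2816. For 0/15 and 5/9, the pooled 5/24 gives 21% (12-33%), against 0% (0-10%) daily and 56% (35-74%) single-dose. The pooled interval overlaps neither. If the rates are equal (5/15 and 3/9), the pooled 8/24 is also 33% and pooling distorts nothing.

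**7. Precision after splitting.** The 80% CI half-width for a mean, in SD units, is t(0.90, n−1)/√n: 2.18 at n = 2, 1.09 at n = 3, 0.60 at n = 6. It cannot be computed at n = 1.

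**The case against.** The strongest reply is that Section 9.7 does not say time interval is the only grouping. It leaves graphics open, and other sections plainly require PK/PD to be judged by level: Section 6.1.2.1 compares effect across doses, and expansion depends on positive results at a given level. A competent team would tabulate by dose anyway. It is true that nothing forbids a dose-level table. But the grouping is stated twice without dose level, and no further analysis document is planned, so following the plan as written produces the mixture.

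It can also be said that the tables are descriptive, the response rates above are assumed, and the counts are minimum-enrolment scenarios that move with expansion and with the allocation rule. All of this stands, and it limits the size of the point. Pooling of 2.5, 5 and 10 mg also begins before Level 4; Level 4 adds the change of schedule and of sampling day.

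Three stronger readings are tempting but unsupported:
- **Compromised decisions.** A reader might infer that escalation or selection for Phase 2 is affected. Section 9.7.1 classifies each patient individually, and the Section 6.1.2 and 6.1.2.1 rules do not draw on these tables.
- **Trough means diluted with zeros.** At Level 4+ the Day 5 pre-dose sample precedes any study everolimus, and Section 5.3 excludes "Prior therapy with ribociclib or any CDK4/6 inhibitor (e.g. palbociclib, abemaciclib), or with everolimus" at therapeutic dosing. Table 13 footnote 11 says "In Dose Level 4+ only, PK blood sampling will occur at the same timepoints", which might suggest pooling with Day 4 troughs. But the footnote is a sampling instruction that goes on to name Day 5 and different hours. Nowhere do the documents say these samples are combined, so no numerical bias can be claimed.
- **No pooled figure is acceptable.** A labelled secondary row beside dose-level rows would mislead no one.

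**Conclusion.** The point holds as a reporting weakness that should be corrected. As written, the Cohort 2 and overall summaries of everolimus, pS6 and PK-/PD-positive status combine two everolimus schedules once Level 4 opens: 10 and 9 patients in Cohort 2, and 15 and 9 overall, at minimum enrolment through Level 6. The tables could not show whether effect rises with dose. Separately, ribociclib by time interval is confounded with dose under the Section 4.1.1 table.

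This rests on Levels 4-6 being opened and, for the cohort-level counts, on the Section 4.1.1 table rather than the Section 6.4.2 rotation; the 15 and 9 overall hold under either. How far a pooled figure misleads depends on how much the schedules differ, which is unknown; if they do not differ, pooling does no harm. No hypothesis test is involved.

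**What to change.** In both grouping sentences of Section 9.7:
- Make dose level the primary grouping for all PK/PD summaries, for both drugs, including the PK-positive and PD-positive proportions.
- Give time interval within dose level. Where a dose-by-time cell has 1-2 patients, list individual values in place of an SD and interval.
- Keep any summary across levels secondary and labelled as pooled. For everolimus, pS6 and PK-/PD-positive status, show it separately for Levels 0-3 (daily) and Levels 4-6 (single dose).
- Tabulate the Day 4 pre-dose samples (trough on daily dosing) separately from the Level 4+ Day 5 pre-dose samples (before the first everolimus dose).

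At the same time, reconcile three descriptions that bear on the table shells. Section 4.1.1 says that all patients take both drugs in five daily doses, although it also lists Levels 4-6. Day 4 sampling is given for Levels 1-3 in Section 4.1.1 and for Levels 0-3 in Section 7.1.1.11.3. The cohort allocation differs between Sections 4.1.1 and 6.4.2.

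The cost is a few sentences, with no extra patients or samples. The downside is imprecision: an 80% CI half-width of 1.09 SD at n = 3 and 0.60 SD at n = 6.
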